The Cold Pressor Test (CPT): This test requires the insertion of the hand into an ice-cold water bath (Techne® water baths, Bibby Scientific US, Burlington, NJ) held at a temperature of 3°C. Participants are instructed to leave their hand in the water bath for at least 1 minute and are told that they may remove their hand earlier if the pain gets unbearable. Maximum immersion time will be 3 minutes. Pain intensity and unpleasantness will be rated every 10 sec during the hand immersion, as well as every 10 sec for 2 minutes and 30 seconds post-testing to capture recovery slopes.

Statistical Considerations

Sample size: 34 subjects (including a 32% discontinuation rate) will run in balanced order through the two protocols, each consisting of a 18-day in-hospital stay (separated by an interval of 1 month or more) in order to complete the study with 26 subjects. **Power calculations** for the inflammatory response (aim 1) were estimated using findings coming from sleep restriction models on IL-6 (plasma levels and expression by monocytes). For the pain-inhibitory response (aim 2), we estimated power using the effects of a single episode of sleep disruption on the pain-inhibitory capacity³⁷. For the recovery response (aim 3), we used data from the effects of recovery sleep on IL-6 positive monocytes, as well as on the habituation to pain in the cold pressor test paradigm (data obtained in currently ongoing protocol). For all 3 aims, optimal power will be reached with a sample size of N=26 (see **Table 1**).

Randomization: Block randomization will be used with block sizes of 10, 8, 8, and 8. Each block will have equal numbers of females and males and equal numbers of sequences (1. insomnia induction – control sleep, 2. control sleep – insomnia induction). Randomization will be prepared by the study statistician and the participant will be informed of the sequence on study day 1.

Statistical Analysis:

Table 2 shows the primary outcome variables for aim 1-3, as well as secondary outcome variables used for explorative analysis (not part of aims).

Some of the variables will be measured at different time scales and reduced to the following summary variables: Subjective estimations of emotional and physical well-being assessed every 4 hours during the waking periods (and after each nighttime awakening during insomnia induction nights) of the protocol will be averaged to nighttime and daytime frequency and intensity measures.

Table 2: Outcome variables			

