Primary outcomes			Secondary outcomes
Aim 1	Aim 2	Aim 3	Explorative
Inflammatory: IL-6, PGE2, resolvins	Pain-inhibitory: CPM	IL-6, PGE2, resolvins, CPM	COX-2, cortisol
Sensitization: HPT, PPT, TS	Habituation: Intensity ratings of HPST	HPT, PPT, TS, HPTS	Emotional/physical well-being
HPT= heat pain threshold; PPT=pressure pain threshold, TS=temporal summation; HPST=heat pain supra- threshold, CPM=conditioned pain modulation, COX=cyclooxygenase			

Table 1: Power calculations.

Variable	Δ Response	Power based on paired Student t-test (α=0.05) – N=26
IL-6 (pg/mL). Response to 10 days of restricted sleep to 4h/night compared to 8h control sleep.	1.95±1.59 pg/ml	>0.80
IL-6 positive monocytes (%). Response to three cycles of sleep restriction (3 x 5 nights of 4 hours of sleep/night), compared to 8h control sleep (ongoing protocol R01 HL 105544, see also Figure 3).	38±66 %	>0.80
Pain inhibition impairment (CPM test, %). Response to 3 days of experimental sleep disruption, compared to control sleep (estimation from graph) ³⁷ .	47±54 %	>0.80

Habituation to pain (CPT test, sec). Response to 3 cycles of sleep restriction (3 x 5 nights of 4 hours of sleep/night), on the ability to habituate to cold pain, compared to 8h control sleep (ongoing protocol R01 HL 105544, see also Figure 7).	-15±25 sec	>0.80
Habituation to pain after recovery sleep (CPT test, sec). Response to 2 recovery nights following 3 cycles of sleep restriction on the ability to habituate to cold pain, compared to 8h control sleep (ongoing protocol R01 HL 105544, see also Figure 7).	-24±28 sec	>0.80

Assessment of Aim 1: Inflammatory response and its relation to indicators of sensitization of the nociceptive system upon repeated episodes of experimentally-induced insomnia symptoms:

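### The claim of optimal power for all three aims rests, for habituation and for recovery, on a cold pressor test that Table 2 does not list as an outcome

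*Combined protocol and SAP*

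**What the plan says.** **Outcomes.** Table 2 lists CPM and "Habituation: Intensity ratings of HPST" as the Aim 2 primaries. Its key expands HPST only as supra-threshold heat pain. Under Aim 3 the item appears as HPTS, presumably the same measure with two letters transposed. The cold pressor test (CPT) is item (3) of the pain testing battery, but it appears in no column of Table 2, primary or explorative.

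**Power.** Table 1 has five rows: plasma IL-6, IL-6 positive monocytes, CPM, and two on habituation. The habituation rows are labelled "Habituation to pain (CPT test, sec" and "Habituation to pain after recovery sleep (CPT test, sec". Both come from an ongoing protocol with three cycles of five nights at 4 hours of sleep. The monocyte row is labelled "IL-6 positive monocytes (%). Response to three cycles of sleep restriction". Under Sample size, Aim 2 power is tied to pain-inhibitory capacity. For Aim 3 the text says "we used data from the effects of recovery sleep on IL-6 positive monocytes", together with cold pressor habituation. It concludes: "For all 3 aims, optimal power will be reached with a sample size of N=26".

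**Tests.** The cold pressor description has ratings every 10 seconds. Participants are "told that they may remove their hand earlier if the pain gets unbearable", and "Maximum immersion time will be 3 minutes". It gives no score in seconds. The battery consists of heat and pressure pain thresholds, temporal summation (TS), CPM and CPT; no test is called HPST. For test details the battery section also refers to Appendix 3, which is not in the supplied text.

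**The concern.** A power statement should concern the outcomes that the trial will test. Here the habituation figures differ from the named primary in modality (cold against heat), in scale (seconds against an intensity rating) and in exposure (4-hour nights in blocks of five against disrupted nights in blocks of three). A reader of the sample size paragraph would think that habituation and recovery had been shown to be adequately powered on the Table 2 outcomes, and they have not.

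The second issue is which heat rating is HPST. The background section describes habituation as ratings that fall when a painful stimulus is repeated from day to day, so the result depends on whether the stimulus stays the same. If the choice is left open until analysis, one of the two Aim 2 primaries could be selected after the data are seen.

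**Working it through.** **1. Reproducing Table 1.** Inputs: the response ± spread in each row, N = 26, paired t-test, α = 0.05. Two assumptions: the spread is the SD of the paired difference, and the test is two-sided (the table does not state either). With d = |Δ|/SD and df = 25, the noncentrality is d × √26 = d × 5.099, and power comes from the noncentral t distribution with critical value 2.060.

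| Row | d | Noncentrality | Power |
|---|---|---|---|
| Plasma IL-6 | 1.95/1.59 = 1.226 | 6.25 | >0.99 |
| IL-6 positive monocytes | 38/66 = 0.576 | 2.94 | 0.81 |
| CPM | 47/54 = 0.870 | 4.44 | 0.99 |
| CPT habituation | 15/25 = 0.600 | 3.06 | 0.84 |
| CPT habituation after recovery | 24/28 = 0.857 | 4.37 | 0.99 |

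All five agree with the stated >0.80. One-sided tests or a normal approximation also leave every row above 0.80.

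**2. Matching rows to aims.**
- Aim 1: IL-6 has rows.
- Aim 2: CPM has a row. The HPST rating has none; the habituation row is CPT.
- Aim 3: the listed outcomes are IL-6, PGE2, resolvins, CPM, HPT, PPT, TS and HPTS. The one row on recovery sleep is CPT after two recovery nights. The monocyte row, named in the text as recovery evidence, measures the response to restriction. The background section does mention monocyte IL-6 failing to return to baseline during brief recovery and points to Figure 3 (not shown), but it gives no figure.

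**3. What N = 26 would give for HPST.** The documents contain no effect or SD for any HPST rating, so the effects below are assumptions, with the same test as in step 1.

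| Assumed d | 0.3 | 0.4 | 0.5 | 0.6 | 0.8 |
|---|---|---|---|---|---|
| Power | 0.31 | 0.50 | 0.69 | 0.84 | 0.98 |

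The smallest effect with 80% power is d = 0.57.

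**4. Which heat rating.** In the Pain testing details, supra-threshold heat ratings arise in the TS sequences (the first test sequence at 48 °C, the next two moved up or down by 1.5 °C according to tolerance) and in the CPM trials at the highest tolerable temperature. Two conditional consequences follow.
- If HPST is rated at a temperature re-tailored at each session, a participant who habituates may be moved to a hotter stimulus, and the fall in ratings can be hidden. The text suggests a restart at 48 °C each session but does not state it, and the size of any masking cannot be computed.
- If HPST is the no-water CPM rating X, and CPM is X − Y with Y the hot-water rating, then Cov(X, X − Y) = Var(X) − Cov(X, Y). In general this is not zero, so the Aim 2 correlation of CPM with habituation would contain a shared term.

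**5. A related inconsistency.** The TS description assigns the highest tolerable temperature to the conditioning stimulus of CPM. The CPM description assigns it to the test stimulus and uses a 47 °C water bath for conditioning.

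**The case against.** Much of the substitution is disclosed. The Sample size text says that cold pressor habituation was used for Aim 3, and Table 1 names the test, unit, exposure and source. Aim 2 power is tied to CPM, which is a Table 2 primary with its own row. Lack of a power row for every primary is not in itself an error. All of this stands. It does not rescue the closing sentence, which covers all three aims without qualification and nowhere argues that cold pressor seconds stand in for heat ratings.

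Material that is not supplied could fill some gaps. Appendix 3 may define HPST, Figure 7 may show how the seconds were scored, and Figure 3 may hold monocyte recovery data. The point about HPST is therefore limited to the supplied text. The mismatch between Tables 1 and 2 does not depend on any of these.

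A reader might infer more than the documents support:
- That the trial is underpowered for habituation. With no HPST effect given, this is unknown; effects as large as those in Table 1 (0.58 to 1.23) would give at least 80% power.
- That Table 1 is miscalculated. It is not.
- That re-tailoring does mask habituation, or that the Aim 2 correlation does share a term. Each holds only under a choice of HPST, or a tailoring rule, that the text leaves open.

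**Conclusion.** The power statement claims more than Table 1 shows. It is supported for the IL-6 and CPM responses. For habituation and recovery it is supported only for the cold pressor test, which has no listed role. It gives no figure for the HPST primary and no recovery figure for any listed Aim 3 outcome. This part rests on the text of Tables 1 and 2 and is held with high confidence. For HPST, 26 completers suffice for 80% power only if the standardized paired effect is at least 0.57, under the paired t-test that Table 1 itself uses.

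That the HPST rating is not identified is held with medium confidence, because Appendix 3 could not be read. The harms from re-tailoring and from a shared term are possible and unquantified. The point should be corrected before analysis; it does not call the design into question.

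**What to change.** 1. Limit the power statement to the IL-6 and CPM responses. Say that habituation and recovery are shown for cold pressor only, as surrogate data from another exposure.
2. List the cold pressor test in Table 2 as a secondary habituation outcome for Aims 2 and 3. Define a score in seconds that states how early withdrawal and the 3-minute cap are handled.
3. Define HPST as one existing heat rating at a temperature held constant within a participant across sessions and both stays, taken outside the CPM trials. If the first pulse of the 48 °C sequence is chosen, disclose that it may also be the rating subtracted to form TS. Use one label in place of HPST and HPTS.
4. Reconcile the TS and CPM descriptions on which stimulus uses the highest tolerable temperature.

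The cost is mainly wording. No new data are needed if the 48 °C sequence is run at every session; if it is not, item 3 needs another constant-temperature rating. The downsides are a less favourable power statement, one more named outcome, and a single rating that is noisier than an average of several.

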will be less than 20lux during wakeful nighttime periods, which is still bright enough to read or play board games with the attending research assistant. These environmental precautions are taken to minimize changes in conditions that can be attributable to body movement or the time-keeping hormone, melatonin. The **sleep control condition** will also be conducted in the CRC. Because the study environment and protocol requirements themselves will have a considerable effect on various behavioral and inflammatory outcome variables, we need to compare the results of our insomnia induction protocol against a sleep control condition. These environmental (CRC)-related effects have occurred in multiple previous studies where we have observed decreases in inflammatory markers while staying in the CRC during control sleep periods^{16,18}.

At least seven days before entering each 18-day in-hospital stay, participants will be asked to follow the study sleep schedule (bedtime 11pm-7am), which will be verified by electronic sleep diary/actigraphy data. The week prior to the 2nd 18-day visit, blood tests used at screening will be repeated to ensure values are in the normal range. Throughout both protocols, participants will be maintained on a balanced diet (NA⁺ and K⁺ controlled) and regimented fluid intake in order to maintain body weight/composition throughout the study. Meals and fluids will be served at regular hours. To prevent sedentary conditions and maintain constant activity levels, participants will take a 10-15 min walk within the CRC or outside on hospital property every couple of hours throughout the waking periods of the protocol (except during induced nighttime awakenings). We will also encourage participants to follow their pre-study exercise habits through a daily opportunity to visit the hospital gym on the non-intensive recording days. Following any gym visits, participants will be allowed *ad libitum* water for up to 1 hour. Participants may have visitors during daytime periods, as well as have access to email and phone, in order to minimize disruptions to their social networks and prevent social isolation. Each study arm will be separated by an interval of 2 months or more. This will allow us to study women during the same menstrual phase in both protocols and provide sufficient time to recovery from residual effects of blood sampling.

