Outcome variables will be measured on 8 out of the 18 in-hospital protocols (baseline, 2nd experimental insomnia/control night and 4th recovery night of each episode, and 3rd recovery night at end of protocol). The analysis will focus on episode-wise comparison of outcome variables between experimental insomnia and control sleep conditions. Although several forms of linear mixed model will be used, our main analysis will focus on daily summary measures (mean, max, min, slope, AUC, etc.) The models will be constructed as follows: the study has two within factors (measurements over several days and measurements within the same day). Data will be used as it is or the difference between the two experimental conditions by episode will be used in the analysis. The main method of data analysis will employ linear mixed model (repeated measures analysis).

By defining appropriate contrast we can evaluate (i) the difference between experimental insomnia nights and recovery sleep nights for the entire study period, (ii) the difference between days 3 and 6 (day6 minus day3), 7 and 10, and 11 and 14 separately. We expect that each of the contrasts will yield a significantly positive value. These comparisons will show if IL-6 values drops or increases from experimental insomnia nights to recovery sleep nights. Similarly, from the same model, by defining appropriate contrasts, we will evaluate the difference between days 6 and 7, 10 and 11, and 14. These contrasts are expected to be negative. Time will also be used as a continuous variable to test the trend and quadratic effect, and if the above contrast does not suggest strong episode-wise effect but mild increment (or decrease) from one episode to the next. We may also use piece-wise regression with a knot at each episode (and also with just one knot to capture the effect of prolonged recovery towards the end of the experiment). As mentioned earlier, many of the exploratory analysis will be guided by plots and summary assessment of the data. Other inflammatory marker (PEG2, resolvins) will be analyzed in a similar fashion.

Sensitization variables (HPT, PPT, TS) will be analyzed similarly and are expected to mimic the time course of inflammatory variables. Correlation between inflammatory markers and sensitization variables will be evaluating using the Altman-Bland method². The linear mixed model described above can be used to obtain the necessary estimates to compute this correlation.

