Assessment of Aim 2: Pain-inhibitory response and its relation to indicators of habituation to pain upon repeated episodes of experimentally-induced insomnia symptoms. Analysis will follow the strategy similar to one outlined in Aim 1. To evaluate co-variation of the pain-inhibitory response with indicators of habituation we will first obtain average values of each value for each day, and use the Altman-Bland correlation approach described earlier.

These data will be analyzed using linear mixed model for doubly repeated measures using SAS GLM procedure as described in:

http://support.sas.com/documentation/cdl/en/statug/63033/HTML/default/viewer.htm#statug_glm_sect054.htm.

Assessment of Aim 3: Recovery of the inflammatory and pain-inhibitory response upon

repeated episodes of experimentally-induced insomnia symptoms. The proposed incomplete resolution of inflammatory and pain-inhibitory responses during the recovery nights and the progressive impairment of these responses across insomnia induction episodes will be evaluated using a mixed model approach and utilizing four time points: baseline, and recovery at the end of 1st, 2nd, and 3rd insomnia episode. Recovery response will be further evaluated by comparing effects of a single night of recovery sleep to a set of 3 nights of recovery sleep at the end of the protocol. Data analysis for this aim is similar to data analysis described for Aim 1, but a different set of contrasts need to be defined. Our conjecture is that during the recovery IL-6 drops but does not reach to the level of previous recovery. To test this we will evaluate contrasts that compare IL-6 values at days 3 and 7, 7 and 11 and 11 and 15. Finally, the difference between day 15 and 17 is assumed to be larger than any other difference between sleep restriction and recovery days. To test this we will evaluate the differences between other recovery days (average of days 7, 11, and 15) and day 17. All analysis will be performed using SAS statistical package (version 9.3).

C. Subject Selection

Human Subjects Involvement and Characteristics

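### The model text for Aims 1 to 3 does not secure the insomnia-versus-control comparison: raw data are allowed without a condition factor, and no contrast names control

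*Combined protocol and SAP*

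**What the plan says.** All references are to section B3 of the combined protocol and SAP.

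- **Intent (Assessment of Aim 1).** "The analysis will focus on episode-wise comparison of outcome variables between experimental insomnia and control sleep conditions".
- **Reason for the control stay (design section, sleep control condition).** The setting itself affects the outcomes, and inflammatory markers fell during control sleep in earlier studies, so "we need to compare the results of our insomnia induction protocol against a sleep control condition".
- **Factors.** The model is built on the statement that "the study has two within factors (measurements over several days and measurements within the same day"). Condition is not listed.
- **Data.** "Data will be used as it is or the difference between the two experimental conditions by episode will be used in the analysis". No rule says which.
- **Aim 1 contrasts.** "the difference between experimental insomnia nights and recovery sleep nights for the entire study period", and "the difference between days 3 and 6 (day6 minus day3), 7 and 10, and 11 and 14 separately". These are expected to be positive. The later step from days 6 to 7 and 10 to 11 is expected to be negative.
- **Aim 3 contrasts.** "To test this we will evaluate contrasts that compare IL-6 values at days 3 and 7, 7 and 11 and 11 and 15". Also: "To test this we will evaluate the differences between other recovery days (average of days 7, 11, and 15) and day 17".
- **Aim 2.** It follows the Aim 1 strategy but cites the SAS GLM procedure for what it calls a linear mixed model.
- **Table 1.** All five rows are responses compared with control sleep, powered by a paired t-test at N=26.

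**The concern.** The quantity of interest is clear from the stated focus, the design rationale and Table 1: the change under insomnia relative to the change under control. The model text does not tie the analysis to it. Two analysts could both follow the Aim 1 paragraph and test different quantities, and Aims 2 and 3 inherit the same text.

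The gap matters because the plan itself reports drift, and in one direction. A fall during the stay would hide an expected rise in IL-6 or PGE2. It could mimic an expected fall, either in resolvins or in IL-6 from insomnia days to recovery days. The reported fall concerns inflammatory markers only. The documents report no such drift for conditioned pain modulation or the pain thresholds.

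**Working it through.** **Inputs from the plan.** Table 1, IL-6-positive monocytes: 38±66, N=26, alpha 0.05, paired t-test. This is the row with least power. A two-sided test is assumed because sidedness is not stated.

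**Assumed inputs.** A fall f between the two compared days of 0, 9.5 or 19 points (0, 25% or 50% of 38), and a correlation r of 0 or 0.5 between a participant's changes in the two stays. The documents give neither. The monocyte row serves as a scale only; the plan does not say that 66 is the SD of any particular day contrast.

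**1. The plan's own figure.** Standardised effect 38/66 = 0.576. Noncentral t with 25 df gives power 0.806. The other rows give more than 0.999 (plasma IL-6), 0.989 (conditioned pain modulation), 0.837 (cold pressor) and 0.987 (cold pressor after recovery). Table 1's claim of more than 0.80 reproduces, for insomnia minus control.

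**2. What each option estimates.** Let the insomnia stay change by 38 − f and the control stay by −f.
- Difference option, or raw data with a condition x day term: (38 − f) − (−f) = 38 for any common fall.
- Raw data, insomnia stay alone: 38 − f.

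**3. SD of a single-stay change.** From 66 = s·√(2(1 − r)), s = 46.7 at r = 0 and 66.0 at r = 0.5.

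**4. Probability of a significant rise, N=26.**

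| Assumed fall | Insomnia stay alone: estimate | Power, r=0.5 | Power, r=0 | Insomnia minus control: estimate | Power |
|---|---|---|---|---|---|
| 0 | 38 | 0.81 | 0.98 | 38 | 0.81 |
| 9.5 | 28.5 | 0.56 | 0.85 | 38 | 0.81 |
| 19 | 19 | 0.29 | 0.51 | 38 | 0.81 |

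**5. False recovery on adjacent-day contrasts (day 7 minus 6).** If 9.5 or 19 points accrue steadily over three days, one day carries 9.5/3 = 3.2 or 19/3 = 6.3 points. With no insomnia effect, the insomnia stay alone shows a significant fall with probability 0.04 / 0.07 (r=0.5) or 0.05 / 0.10 (r=0), against a nominal 0.025.

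**6. Contrast days against recording days.** Night 3 is baseline, so the first episode is nights 4 to 7. The intensive recordings fall on the 2nd and 4th day of each episode, which are two days apart. The contrasts use days 6 and 7, and 10 and 11, which are one day apart. Both cannot hold under a single day numbering.

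**7. GLM.** In multivariate repeated form, GLM keeps only participants with every value. Over 8 days x 2 stays, with an assumed 2% of daily values missing, 0.98^16 = 0.724, so about 19 of 26 remain. Power for the conditioned pain modulation row (47±54) goes from 0.99 to 0.95.

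**The case against.** The best defence is that the focus sentence settles the matter and one of the two data options already is the remedy. Once differences are taken, condition is absorbed, and listing only day and time of day is correct. This stands. A reader might infer that the plan has no control comparison; the documents do not support that. What remains is an unregulated choice in which one permitted branch loses the comparison.

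A reader might also infer that both stays would be pooled with no condition term, which would halve the effect to 19 before any drift. The text does not expressly exclude this, but it argues against it: the first Aim 1 contrast compares insomnia nights with recovery nights, and the control stay has neither. The insomnia stay alone is the more natural reading.

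The drift sizes are assumptions. The plan reports a direction but no size or timing, and some of the fall may occur in the two adaptation days before baseline. That is why the range includes zero. High false-recovery rates cannot be claimed for the overnight contrasts: they would require a three-day fall to happen in one day.

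A missing period term might be read as biasing the listed contrasts. It does not, because a period effect that is constant over a stay cancels in every within-stay difference, and sequences are balanced by block. The GLM point is chiefly a mismatch between label and procedure; the power loss rests on assumed missingness and is modest.

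**Conclusion.** The point holds in this limited form and should be fixed. The plan states the right comparison, but its model and contrasts do not secure it. Under the raw-data option, read as the insomnia stay alone, the estimate shifts one for one with in-hospital drift. On the 38±66 row, an assumed fall of 9.5 to 19 points takes power from 0.81 to between 0.56 and 0.29 at r=0.5, and from 0.98 to between 0.85 and 0.51 at r=0. False overnight recovery rises to about 0.04 to 0.10 against 0.025. These figures illustrate the exposure and do not estimate it. Insomnia minus control is unaffected by any fall common to both stays. Table 1's power at N=26 is not in dispute.

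**What to change.** - Replace the sentence that offers raw data or differences with one linear mixed model (PROC MIXED) on the undifferenced daily values of both stays. Use condition, day and condition x day as fixed effects, participant-level covariance, and all available data.
- Define every Aim 1 to 3 contrast as the insomnia change minus the control change between the same two recorded days. First reconcile contrast days 6, 10 and 14 with the recording schedule.
- Use the same model for Aim 2 in place of the GLM reference.
- Minor: add a period term. It matters only for comparisons of condition levels.

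**Cost.** SAP wording only, in the SAS package already named. The period term takes about one degree of freedom: power on the weakest row goes from 0.806 to 0.804 with sequences split 13/13. Undifferenced data also keep participants who complete only one stay, whom the difference option drops. If there were no drift and the stays were uncorrelated, the insomnia stay alone would have more power (0.98 against 0.81), but it would not be a comparison with control.

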In case of last-minute cancellations of the 18-day in-hospital stays, we will attempt to fill the open slots with new participants. We will use adaptation day 1 of the study for screening purposes (i.e., initial and medical/overnight screening), and if fulfilling screening criteria, the participant will continue the following day with adaptation day 2 of the study.

Visit 5: Follow-up. Seven to 14 days following their final discharge from the CRC (after completing both study protocols), participants will return to the CRC to have a final blood draw to ensure that any potential activation of the blood markers have returned to baseline and to review their study experience.

Participants.

We anticipate screening 612 subjects in order to have 34 participants with an attrition rate of 32% complete both 18-day in-hospital study protocols. We typically screen 18 potential participants for every one that enters the in-hospital part of the study. In our experience with 2 25-day in-hospital stays separated by a monthly interval, we have an attrition rate of 32%. As such, 34 participants will need to enter the hospital phase to have 26 participants complete 2 18-day in-hospital protocols.

Procedures.

Model of repeated exposure to experimentally-induced insomnia symptoms. The hypothesis will be tested within an experimental insomnia model characterized by (1) induction of insomnia symptoms for 3-day long episodes, and (2) the repeated nature of such insomnia episodes, i.e. after a night of good sleep, the next episode will start. Participants will undergo 3 of those 3-day episodes of insomnia symptom induction, each followed by 1 night of 8 hours of sleep. Such patterns are

commonly experienced in individuals suffering from insomnia, where intervals of 1 to 3 nights of poor sleep are followed by a night of good sleep, likely due to the buildup of sleep pressure during the interval of poor sleep^{31;41}. The advantage of this approach is that it mimics sleep-wake patterns frequently found in the general population for a number of reasons, and in chronic pain populations in particular^{28;39}. In contrast to previous studies, mostly using single episodes of sleep restriction or deprivation, this approach will facilitate the translation of findings directly into clinical applications.

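### The plan leaves open a main analysis on condition differences, and names SAS GLM for Aim 2; both drop participants without a second stay, 8 to 11 of the 34 entrants

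*Combined protocol and SAP*

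**What the plan says.** - **Data set (B3, Assessment of Aim 1).** Two options stand side by side. The first is the data as recorded; under the second, "the difference between the two experimental conditions by episode will be used in the analysis". Nothing says which is primary or what decides between them.
- **Method (same section).** "The main method of data analysis will employ linear mixed model (repeated measures analysis"). The factors named are day and time within day. No period or sequence term is named.
- **Procedure (Assessment of Aim 2).** The Aim 2 model is described as a linear mixed model for doubly repeated measures, but the SAS procedure named to fit it is GLM.
- **Expected loss (Participants).** "In our experience with 2 25-day in-hospital stays separated by a monthly interval, we have an attrition rate of 32" per cent, and "34 participants will need to enter the hospital phase to have 26 participants complete 2 18-day in-hospital protocols". The Sample size text repeats the rate: "34 subjects (including a 32% discontinuation rate) will run in balanced order through the two protocols".
- **Allocation (Randomization).** "Each block will have equal numbers of females and males and equal numbers of sequences", so the two sequences start level.
- **Entry to the second stay (Visit 3 and 4).** "The week prior to the 2nd 18-day visit, blood tests used at screening will be repeated to ensure values are in the normal range".

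The documents define no analysis population, give no rule for a missing stay, and plan no comparison of withdrawal between sequences.

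**The concern.** A participant who leaves after the first stay has no insomnia-minus-control difference, so the paired option removes that person entirely, including up to 8 intensive recording days already collected. Fitting a mixed model to the differences does not help, because the loss occurs when the difference is formed. A multivariate repeated-measures GLM likewise keeps only people with complete data.

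Two things are at stake. One is precision. The other is selection: insomnia-first participants decide whether to return after a stay with 9 disrupted nights (3 episodes of 3), and control-first participants decide after undisturbed sleep. If outcome influences return in one sequence and not in the other, the completers' difference no longer estimates the effect in everyone randomized. With the choice of data set open, it could also be made after results are seen.

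**Working it through.** **1. How many entrants lack a second stay.** The plan's figure is 34 entrants for 26 completers at 32% attrition.
- 26 / (1 − 0.32) = 38.2, so 39 entrants; 34 is not reproduced this way. 26 × 1.32 = 34.3 comes close and is probably its origin.
- As planned: 34 − 26 = 8 lost, and 8/34 = 23.5%.
- At the stated rate: 0.32 × 34 = 10.9, about 11 lost.

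The two figures disagree, so I carry both: 8 to 11 people. At 8 recorded days each this is at most 64 to 88 days, reached only if every leaver finishes the first stay.

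**2. Precision under random drop-out.** Simulated 34-person crossover, about 32% leaving after stay 1, between-stay correlation ρ assumed 0.5 or 0.7:

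| ρ | SE, completers' paired difference | SE, all entrants (condition and period) | Reduction |
|---|---|---|---|
| 0.5 | 0.209 | 0.198 | 1 − 0.198/0.209 = 5% |
| 0.7 | 0.159 | 0.153 | 1 − 0.153/0.159 = 4% |

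**3. Bias under selection in one sequence.** None of these inputs is in the documents: true effect 0.5 SD; ρ 0.5 or 0.7; equal drop-out rates in the two sequences; drop-out in the insomnia-first sequence following a logistic curve in the stay-1 outcome with slope 1 or 1.5 per SD (odds ratio 2.7 or 4.5); random drop-out in the control-first sequence.

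Let s be the mean standardized stay-1 outcome among insomnia-first completers. Their insomnia value shifts by s and their control value by ρs, so their mean difference shifts by (1 − ρ)s. Control-first completers are unshifted. With equal completion the overall bias is (1 − ρ)s/2.

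| Drop-out | Slope | s | Bias, ρ = 0.5 | Bias, ρ = 0.7 |
|---|---|---|---|---|
| 23.5% | 1 | −0.20 | −0.05 | −0.03 |
| 23.5% | 1.5 | −0.26 | −0.07 | −0.04 |
| 32% | 1 | −0.27 | −0.07 | −0.04 |
| 32% | 1.5 | −0.35 | −0.09 | −0.05 |

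The understatement is therefore about 0.03 to 0.09 SD, or 6% to 18% of a 0.5 SD effect. In a simulation of 400,000 people at 32%, a likelihood-type model on all entrants with condition and period was within 0.004 SD of the truth.

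**4. The same selection in both sequences.** The control-first shift is then −(1 − ρ)s and cancels the insomnia-first shift. The simulation agrees: the paired bias was about 0.001 SD or less.

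**5. Unequal withdrawal rates alone.** With 54% and 10% leaving in the two sequences, unrelated to outcome and with no period effect, the bias is within 1% of the effect. With an assumed period effect of 0.3 SD and no period term, it is +0.05 SD (44%/20% leaving) to +0.09 SD (54%/10%). Hence the period term in the fix.

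**6. Selection on the person's own difference.** If leaving depends on the participant's insomnia-control difference, which is unobserved at withdrawal, the paired estimate is low by 23-26%. A likelihood model that keeps first-stay data is still low by 14-22%.

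**The case against.** The strongest reply is that the plan already offers the better analysis. Using the data as recorded is the first option listed, a linear mixed model is the named main method, and Aim 3 also calls for a mixed model. On that view this is a request for precision. The reply stands in part: a sound analysis is available within the plan. But the plan equally permits a complete-case one, Aim 2 points to GLM, and the power calculation is a paired t-test on 26 completers, so nothing commits the trial to keeping one-stay participants.

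A reader might go further and infer that unequal withdrawal after the insomnia stay will bias the result. The documents do not support that. They report no withdrawal by sequence or by outcome, and steps 3 and 5 show that unequal rates are neither necessary nor sufficient. The stay also includes recovery nights between episodes and at the end, and the pain battery is given in both conditions.

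Nor do the documents show that the blood re-check selects on outcome. The screening tests listed are blood count with differential, thyroid hormone and glucose, not IL-6, PGE2 or pain.

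The size is also modest. At 32% drop-out the bias is under half the paired standard error (0.09 against 0.209; 0.05 against 0.159), and under the assumed selection it runs toward no effect. The 32% itself comes from longer, 25-day stays.

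**Conclusion.** The point holds in conditional form. The plan permits a main analysis, and for Aim 2 names a procedure, that discards the first-stay data of 8 to 11 of 34 entrants, with no rule for choosing otherwise. The cost is about 4-5% in standard error under random drop-out. The possible bias is an understatement of about 0.03-0.09 SD on a 0.5 SD effect. That bias rests on assumed outcome-related withdrawal in the insomnia-first sequence only, odds ratios of 2.7 to 4.5 per SD, and correlations of 0.5 to 0.7; it is zero if selection is the same in both sequences. The documents give no evidence on which situation applies, so this is not a finding that the planned estimate is biased. It is a reason to settle the analysis in advance, since the better method is already within the plan's reach.

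**What to change.** 1. **Assessment of Aim 1:** make a likelihood-based linear mixed model on the raw values, with condition, day and period, the main analysis. State that every randomized participant with at least one recorded day in either stay is included, whether they leave during or after the first stay or do not pass the repeat blood tests. Remove the difference option from the main analysis.
2. **Assessment of Aim 2:** replace the GLM procedure with the same likelihood-based mixed model.
3. Keep the completers' paired difference as a sensitivity analysis.
4. Tabulate withdrawals and failed pre-stay-2 blood checks by sequence.

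The cost is revised wording and a little more analysis, with no added participants or measurements. The model relies on drop-out being explained by observed data. If leaving depends on a person's unobserved insomnia-control difference, bias is only partly removed (step 6), which is why items 3 and 4 matter. People who leave partway through the first stay contribute only the days they completed.
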